6.2 Medical and procedure history

6.2.1 Medical history diseases

The summary of medical history will be based on the medical history at the time of entry into the previous study.

The number and percentage of subjects with a medical history condition, including both resolved and ongoing conditions at the time of entry into the previous study, will be summarized overall and by primary MedDRA system organ class (SOC) and preferred term (PT) for the Safety Analysis Set.

6.2.2 Procedure history and concomitant procedures

Medical procedures are not coded and will only be provided in subject data listings.

6.3 History of epilepsy

All of the following are summarized using data collected at the time of entry into the previous studies or from the Baseline Period of the previous studies.

6.3.1 Etiology of epilepsy

The number and percentage of subjects with each type of etiology as specified on the CRF (genetic, congenital, etc) from the previous studies will be summarized for the Efficacy Analysis Sets for POS and PGS. A subject will be counted as having a particular etiology if that etiology was either confirmed or suspected based on the investigator's assessment. Etiology of epilepsy is not collected for subjects from previous study N01258.

6.3.2 Epileptic seizure profile

The number and percentage of subjects experiencing each seizure type at any time prior to study entry will be summarized for the Efficacy Analysis Sets for POS and PGS. The following seizure types will be summarized: I, IA, IA1 through IA4, IB, IB1, IB2, IC, II, IIA through IIF, III. A subject with a history of a more specific seizure type will be counted in all higher levels of seizure types (eg, a subject with a history of IB1 seizures will be counted for seizure types I, IB, and IB1).

6.3.3 Classification of epileptic syndrome

The number and percentage of subjects with each epileptic syndrome will be summarized for the Efficacy Analysis Sets for POS and PGS. This summary will include the number and percentage of subjects within the following categories: localization-related epilepsy; idiopathic, symptomatic, and cryptogenic localization-related epilepsy; generalized epilepsy; and idiopathic, symptomatic, and cryptogenic generalized epilepsy.

6.3.4 Focus localization

The number and percentage of subjects with each category of focus localization (unknown, frontal, temporal, parietal, occipital) will be summarized for the Efficacy Analysis Set for POS. Subjects may be counted in more than 1 category of focus localization. A category for no available data will be included in the summary to account for subjects from N01258 since focus localization was not obtained for subjects from N01258. Percentages will still be out of the full POS Efficacy Analysis Set, including subjects from N01258.

6.3.5 History of epileptic seizures

History of epileptic seizures, including the number and percentage of subjects with a history of status epilepticus and quantitative summaries of epilepsy duration, age at onset of first seizure, and percent of life with epilepsy, will be summarized for the Efficacy Populations for POS and PGS.

6.3.6 Seizure types experienced during baseline of the prior study

The number and percentage of subjects experiencing each seizure type during the Baseline Period will be summarized for the Efficacy Analysis Sets for POS and PGS based on the Baseline seizure diary data from the previous studies. The following seizure types will be summarized: I, IA, IB, IC, II, and IIA through IIF, and III as well.

Subjects will be counted for all higher levels of seizure type categories corresponding to the seizure types or seizure sub-types reported on the CRF.

6.4 Medications

Medications recorded on the Concomitant Medications CRF and the Concomitant Medications (AEDs only) CRF will be classified as either AEDs or non-AEDs based on the preferred drug name search criteria, which are documented outside of the SAP.

- The medication is not an AED if it does not meet the search criteria based on preferred drug name, regardless of which CRF is used for reporting the medication. However, further review will be performed for medications that are recorded on the Concomitant Medications (AEDs only) CRF but are not included in the AEDs search criteria;
- For non-benzodiazepine medications, if the medication meets the search criteria for an AED based on preferred drug name, then the medication will be classified as an AED regardless of indication and regardless of which CRF the medication is recorded on;

- For benzodiazepines (identified using the search criteria), if the benzodiazepine is recorded on the Concomitant Medications (AEDs only) CRF, then the benzodiazepine will be classified as an AED;
- For benzodiazepines (identified using the search criteria), if the benzodiazepine is recorded on the Concomitant Medications CRFs, then the benzodiazepine will not be classified as an AED.

After medications are classified as AEDs or non-AEDs, the standard date imputation algorithms for start and stop date of the medication and first dose and last dose of BRV in the study will be applied. If an AED was taken at any time during dosing with BRV, then the AED is classified as a concomitant AED.

6.4.1 Non-AEDs taken at study entry

The number and percentage of subjects taking non-AED medications at study entry for the previous double-blind study will be summarized by WHO-DRL primary therapeutic group (Anatomic Therapeutic Class [ATC] level 1), therapeutic subgroup (ATC level 2), and preferred drug name for the Safety Analysis Set.

6.4.2 Number of previous AEDs

The number and percentage of subjects taking an AED prior to entry into the previous study will be summarized by WHO-DRL preferred drug name for the POS and PGS Efficacy Analysis Sets based on the following categorization: 0-1 AEDs, 2-4 AEDs, and ≥ 5 AEDs.

6.4.3 History of previous AED use

The number and percentage of subjects who had taken at least 1 AED prior to entry into the previous study will be summarized overall and by WHO-DRL preferred drug name for the POS and PGS Efficacy Analysis Sets.

6.4.4 AEDs taken at study entry

The number and percentage of subjects taking AEDs at study entry for the previous double-blind study will be summarized by WHO-DRL preferred drug name for the POS and PGS Efficacy Analysis Sets.

6.4.5 Concomitant AEDs

A concomitant AED is an AED which was taken during administration of BRV in N01379 study, regardless of the start and stop date of the AED. The number and percentage of subjects taking concomitant AEDs will be summarized by WHO-DRL preferred drug name for the POS and PGS Efficacy Analysis Sets.

7 MEASUREMENTS OF TREATMENT COMPLIANCE

Study drug compliance will not be assessed due to the complexities associated with the calculation and interpretation of study drug compliance for this study. Study drug dosing will be provided in subject data listings.

8 EFFICACY ANALYSES

In general, all study outcomes based on seizure frequency will be summarized for the Efficacy Analysis Set for POS and all study outcomes based on seizure days will be summarized for the Efficacy Analysis Set for PGS.

The derivations of 28-day adjusted seizure frequency and 28-day adjusted seizure days are described in detail in Section 3.8.1.2 and Section 3.8.1.3, respectively.

All summaries of efficacy data are descriptive; no statistical testing will be performed.

Because study N01258 was a safety study, subjects were not required to meet seizure frequency requirements during the Baseline Period, and the Baseline Period was short (ie, 7 days). Therefore, subjects from N01258, whether subjects with POS or PGS, will be excluded from efficacy summaries in the variables of percent reduction in POS frequency and responder rates, but subjects from N01258 will be included in the efficacy summary in the variable of the percent of subjects continuously seizure free as this variable is independent from baseline.

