3.2.4 Study periods

The Baseline Period for N01379 corresponds to the Baseline Period of the previous studies, and is defined for seizure outcomes and direct cost parameters. The Baseline Period is defined as study days on or after the date of Visit 1 and prior to the date of Visit 2 for N01258 and study days on or after the date of Visit 1 and prior to the date of Visit 3 for N01358.

The study is divided into 3 periods: Evaluation Period, Down-Titration Period, and Post-Treatment Period. A subject is classified as “discontinued” if the subject has a termination case report form (CRF) or has an early discontinuation visit (EDV). A subject is classified as “completed” if this subject completes the full extent of the study as defined in the protocol at database lock.

A “discontinued” subject can be potentially slotted into the 3 periods of the study. The following algorithms will be used to slot the subject appropriately into the Evaluation Period, Down-Titration Period, and Post-Treatment Period.

- For Evaluation Period, the start date is the date of first dose of BRV, and the following algorithm is used to determine the end date:
 - If the subject enters the Down-Titration Period, then the date of EDV is the end date;
 - If the subject does not enter the Down-Titration Period but meets 1 of the following criteria, the Evaluation Period ends on date of last dose of BRV:
 - Without an EDV but having a termination CRF,
 - With an EDV and having a termination CRF,
 - With an EDV and the date of EDV prior to the database lock date and having no termination CRF.

- A subject is considered entering Down-Titration Period only if the subject has an EDV and at least 1 dose of study drug after the date of EDV, the start date of Down-Titration Period is set as 1 day after the date of EDV, and the Down-Titration Period ends on date of last dose of BRV. A subject without an EDV but having a termination CRF or with an EDV but without any dosing of study drug after the EDV will not have the Down-Titration Period, and no artificial Down-Titration Period will be created for analysis.
- A subject is considered entering the Post-Treatment Period if the subject has at least 1 contact (scheduled visit, unscheduled visit, or telephone contact) after the date of last dose of BRV. The Post-Treatment Period starts 1 day after date of last dose of BRV irrespective of entering the Down-Titration Period, and there is no end date.

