3.5.2 Efficacy populations

Efficacy Populations will consist of all subjects who took at least 1 dose of study drug and have at least 1 seizure diary day during the Evaluation Period. Separate Efficacy Populations are defined for subjects with focal epilepsy from N01358 and N01258 and subjects with generalized epilepsy from N01258.

A subject will be excluded from the Efficacy Analysis Set for POS or PGS if either they did not receive at least 1 dose of BRV, or the clinical database indicates that the daily seizure diary was not completed for any days on or after the first dose of BRV and on or prior to the end date of the Evaluation Period (see Section 8). Subjects were assigned to a POS population or a PGS population in the previous study, based on diagnosis or medical history.

Seizure outcomes will be summarized for either the Efficacy Population for POS or the Efficacy Population for PGS. Summaries of epilepsy history and QOLIE-31-P will be provided for the Efficacy Populations for both POS and PGS.

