8.1.1 Partial onset seizure frequency

Twenty-eight day adjusted POS frequency will be summarized with quantitative descriptive statistics for all subjects for the Baseline Period, the On Treatment Period, and by 3-month time intervals over the On Treatment Period. The summary over the On Treatment Period will include all subjects in the POS Efficacy Analysis Set. Similar summaries will be provided for the full cohort interval and by 3-month time intervals for each exposure duration cohort.

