8.2.2.1 All type seizure days

Twenty-eight day adjusted all other type seizure days will be summarized with quantitative descriptive statistics in the same manner as 28-day adjusted POS frequency.

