8.2.2.2 Percent reduction in all type seizure days

Percent reduction in all other type seizure days from Baseline will be calculated in the same manner as percent reduction in POS frequency as described in Section 8.1.2. This variable will be summarized in the same manner as percent reduction in POS frequency.

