8.2.2.3 Responder outcome for all type seizure days

Responder outcome for all other type seizure days will be derived in a manner similar to the responder outcome for POS frequency as described in Section 8.1.3. This variable will be summarized in the same manner as 50% responder outcome for POS frequency.

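### The planned responder outcome for generalized-epilepsy (PGS) subjects has no eligible subjects, and the SAP leaves open whether their percent reduction is barred too

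*SAP*

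**What the plan says.** **Who is in the PGS set.** SAP 3.5.2: "Separate Efficacy Populations are defined for subjects with focal epilepsy from N01358 and N01258 and subjects with generalized epilepsy from N01258". The other feeder study, N01358, enrolled only refractory partial-onset seizures (SAP 2.3), so it supplies no PGS subjects.

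**The bar.** SAP 8 gives two reasons for treating N01258 differently: as a safety study it set no seizure-frequency requirement during baseline, and that baseline lasted 7 days. SAP 3.2.4 defines it as the days "on or after the date of Visit 1 and prior to the date of Visit 2 for N01258". N01258 subjects, "whether subjects with POS or PGS, will be excluded from efficacy summaries in the variables of percent reduction in POS frequency and responder rates", are therefore left out. They stay in the seizure-freedom summary, "as this variable is independent from baseline". Protocol 12.4 also bars N01258 from responder rates because of the short baseline. It does not mention percent reduction.

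**What is still planned for PGS.** Protocol 4.2.2 and SAP 2.2.2.2 list both percent reduction and responder rate for type II seizure days. SAP 8.2.2.3: "Responder outcome for all other type seizure days will be derived in a manner similar to the responder outcome for POS frequency". SAP 8.2.2.2 takes its calculation from 8.1.2 and adds: "This variable will be summarized in the same manner as percent reduction in POS frequency". SAP 8.2.2.1: "Twenty-eight day adjusted all other type seizure days will be summarized with quantitative descriptive statistics", following the POS layout in 8.1.1, which is "for all subjects for the Baseline Period, the On Treatment Period, and by 3-month time intervals over the On Treatment Period".

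**The concern.** Two instructions in the same chapter cannot both be followed. One bars every N01258 subject from responder rates and names PGS subjects expressly. The other asks for a responder outcome in a population made up only of N01258 subjects.

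Percent reduction has a different problem. The bar's wording covers POS frequency, not seizure days, while its reasoning covers both. Two programmers working from this SAP could properly produce different outputs. If the PGS table is produced, each subject's result is divided by a 7-day count that may be zero, and the 8.1.2 formula says nothing about that case.

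At stake are one empty table and one table that could mislead in either direction, for variables the protocol commits to reporting.

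**Working it through.** There is no sample-size or power figure in the plan to reproduce, and no hypothesis tests are planned.

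**Step 1. Responder denominator.**

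| Source study | PGS subjects supplied | Left after the Section 8 bar |
|---|---|---|
| N01358 | 0 (POS only) | 0 |
| N01258 | at most 100 (Protocol 5.1.2; the 100 also includes focal subjects) | 0 |
| Total | at most 100 | **0** |

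The result does not depend on enrollment. Treating 8.2.2.3 as the more specific text that overrides Section 8 does not work. Percent reduction in POS frequency is summarized only for the POS set, so the mention of PGS subjects in the bar can take effect only through responder rates. Exempting 8.2.2.3 would leave those words with no effect.

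**Step 2. What a 7-day baseline can show.** If B is the number of seizure days in 7 completed diary days, the 28-day value is 28B/7 = 4B. The only possible values are 0, 4, 8, ..., 28. The 8.1.2 formula divides by this value and is undefined when B = 0.

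**Step 3. Size of the distortion (illustration).** The documents give no PGS seizure-day rate, so the rates r below are assumptions. Days are taken as independent, with no true change on treatment:

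- B ~ Binomial(7, r/28)
- P(B = 0) = (1 - r/28)^7
- apparent percent reduction for B ≥ 1 is 100 × (1 - r/(4B)), averaged over B ≥ 1

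For r = 1, P(B = 0) = (27/28)^7 = 0.775, and a subject with B = 1 shows 100 × (1 - 1/4) = +75% with no change at all. For r = 12, a subject with B = 1 shows 100 × (1 - 12/4) = -200%.

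| True seizure days per 28 | Zero baseline | Mean apparent reduction, the rest |
|---|---|---|
| 1 | 77.5% | +76.3% |
| 2 | 59.5% | +55.4% |
| 4 | 34.0% | +21.7% |
| 6 | 18.5% | -1.4% |
| 8 | 9.5% | -15.3% |
| 12 | 2.0% | -22.2% |

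Simulating the on-treatment days as binomial over 90, 360 or 720 days (r = 1, 2, 4, 8, 12) moves each mean by at most 0.2 points. The medians behave differently:

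| Rate | Median over 90 / 360 / 720 days |
|---|---|
| 1 | +76.7 / +76.7 / +75.7 |
| 4 | +22.2 / +12.5 / +8.6 |
| 8 | +2.8 / +1.8 / +1.3 |
| 12 | +1.5 / +0.2 / +0.2 |

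If seizure days cluster (beta-binomial baseline, assumed within-subject correlation 0.3), the zero share and mean are 87.7% and +82.8% at rate 1, 58.0% and +38.7% at rate 4, 31.7% and -2.6% at rate 8, and 16.0% and -25.2% at rate 12.

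**Step 4. Which seizure variable.** The headings of 8.2.2.1 to 8.2.2.3 refer to *all type* seizure days. Their text refers to *all other type*, which is nowhere defined. SAP 2.2.2.2 specifies type II. SAP 3.8.1.3 counts unclassified (type III) seizures as PGS, yet derives only type II and I+II+III, with no II+III variable.

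**The case against.** The strongest reply is that this is leftover text and not a plan that would yield a wrong result. Section 8 opens the efficacy chapter and names PGS subjects, and Protocol 12.4 and the Protocol Summary repeat the responder bar. A sensible programmer would skip the table, and no estimate would be biased. For percent reduction, Section 8's reasons apply equally to PGS, and the one variable it expressly keeps is seizure freedom. The Protocol Summary's list for generalized-epilepsy subjects contains neither percent reduction nor responder rate, although that Summary still names a primary efficacy variable and seems to predate the current arrangement of variables. Protocol 12.4 also allows generalized-epilepsy variables to be dropped.

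Much of this bears on weight and is accepted. The percent-reduction half is an ambiguity, not a clear intention to use a rejected baseline. The illustration rests wholly on assumed rates. The apparent worsening at high rates is a feature of the mean: the medians at rates 8 and 12 stay between about 0 and +3%, and SAP 3.1 plans medians and quartiles as well.

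The contradiction remains. The Protocol 12.4 allowance turns on the number of subjects, whereas the bar turns on baseline length; 50 PGS subjects would still give a responder denominator of 0. The undefined zero baseline and the inflation at low rates affect medians as well as means.

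**Conclusion.** The concern holds, as a minor internal inconsistency.

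- **Responder outcome:** the denominator is 0 under the current text. This needs no assumption.
- **Percent reduction:** the text supports two readings. On the literal one, the summary uses a baseline that the SAP itself considers unfit and has no zero-baseline rule. How large the distortion would be depends on seizure-day rates that the documents do not give.

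Both are descriptive variables listed as other efficacy, in an unstated part of at most 100 N01258 subjects, in a study whose primary objective is safety. PGS seizure freedom and QOLIE-31-P change from Baseline are unaffected. No dilution of the POS responder rate is claimed: SAP 8.1.2 and 8.1.3 refer to the whole POS set, which includes N01258 focal subjects, but Section 8 probably governs there already.

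**What to change.** 1. In SAP 8, extend the exclusion to percent reduction in POS frequency or in seizure days, and responder rates.
2. Delete SAP 8.2.2.2 and 8.2.2.3 and the two matching bullets in 2.2.2.2.
3. Record the departure from Protocol 4.2.2 with both Section 8 reasons (7-day baseline, no seizure-frequency requirement). SAP 2.2.2.3 already does this for the pharmacoeconomic variables.
4. Clean up the wording. In 8.1.2 and 8.1.3, restrict the summaries to N01358 subjects in the POS Efficacy Analysis Set. In 8.2.2.1, name type II seizure days as the variable, with I+II+III supportive. In 3.8.1.3, state whether type III seizure days count in the PGS variable.

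Deletion follows the SAP's own reasoning but is not the only consistent choice. If the sponsor prefers to keep either outcome, it must exempt PGS subjects with a stated reason and add a zero-baseline rule.

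The cost is SAP wording and fewer PGS tables. What is lost is the baseline-relative seizure summaries for PGS. PGS subjects keep 28-day adjusted seizure days at Baseline and On Treatment, continuous seizure freedom, and QOLIE-31-P change.

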8.1 Statistical analyses of secondary efficacy variables

The following variables are summarized for the Efficacy Population for POS.

8.1.1 Partial onset seizure frequency

Twenty-eight day adjusted POS frequency will be summarized with quantitative descriptive statistics for all subjects for the Baseline Period, the On Treatment Period, and by 3-month time intervals over the On Treatment Period. The summary over the On Treatment Period will include all subjects in the POS Efficacy Analysis Set. Similar summaries will be provided for the full cohort interval and by 3-month time intervals for each exposure duration cohort.

8.1.2 Percent reduction in POS frequency

Percent reduction in POS frequency from Baseline to the On Treatment Period will be calculated as follows, where On Treatment Period Frequency is the 28-day adjusted POS frequency during On Treatment Period and Baseline Period Frequency is the 28-day adjusted POS frequency during the Baseline Period of the previous study.

$$\% \text{ Reduction} = 100 \times \frac{\text{Baseline Period Frequency} - \text{On Treatment Period Frequency}}{\text{Baseline Period Frequency}}$$

A similar calculation applies to each 3-month time interval over the On Treatment Period and for the cohort interval for each exposure duration cohort.

Percent reduction from Baseline for POS frequency will be summarized with quantitative descriptive statistics for the On Treatment Period, and by 3-month time intervals over the On Treatment Period. The summary over the On Treatment Period will include all subjects in the POS Efficacy Analysis Set. Similar summaries will be provided for the full cohort interval

and by 3-month time intervals for each exposure duration cohort. Percent reduction from Baseline for POS frequency will be summarized in the same manner by geographic region.

8.1.3 Responder outcome for POS frequency

Responders over the On Treatment Period are defined as subjects with a 50% or greater reduction in 28-day adjusted POS frequency from Baseline to the On Treatment Period. A similar calculation applies to each 3-month time interval over the On Treatment Period and for the cohort interval for each exposure duration cohort.

The number and percentage of responders for POS frequency will be summarized for the On Treatment Period, and by 3-month time intervals over the On Treatment Period. The summary over the On Treatment Period will include all subjects in the POS Efficacy Analysis Set. Similar summaries will be provided over the full cohort interval and by 3-month time intervals for each exposure duration cohort. Responder rates for POS frequency will be summarized in the same manner by geographic region.

